### **5.13.3. Deaths, Other Serious Adverse Events, and Other Notable Adverse Events**

An overview of AEs, including the number and percentage of subjects who died, suffered SAEs, discontinued due to AEs and who suffered TEAEs, will be provided. Comparison between treatments will be performed using Fisher's exact Test.

In addition, the proportion of subjects within specific clusters of TEAEs will be summarized and treatment comparisons will be conducted using Fisher's exact Test. Clusters will be created from MEDRA's High Level Group Terms (HLGT) ([Table LLCF.SAP.3](#)). Each of the 3 groups with multiple HLGTS will be combined to form one cluster. Additionally, the 2 HLGTS in the skin disorder group will be analyzed separately.

**Table LLCF.SAP.3. Adverse Events of Special Interest**

AE Groups of Interest	MedDRA Search Strategy
Nervous System Disorders	Neuromuscular Disorders HLT
Eye Disorders	Retinal disorders SMQ
Skin Disorders	Hypopigmentation disorders HLT Pigmentation changes, NEC HLT Epidermal and Dermal Conditions HLT
Liver Disorders	Drug related hepatic disorders – comprehensive search SMQ
Cardiovascular-type events - Arrhythmic	Arrhythmia related investigations, signs and symptoms SMQ Cardiac arrhythmia terms (incl. bradyarrhythmias and tachyarrhythmias) SMQ TdP/QT prolongation SMQ
Cardiovascular-type events - Ischemic	Ischaemic heart disease SMQ
Cardiovascular-type events – Stroke	Central nervous system vascular disorders SMQ
Vascular Disorders	Decreased and Nonspecific Blood Pressure Disorders and Shock HLT

Abbreviations: AE = adverse event; HLT = high-level group term; HLT = high-level term; MedDRA = Medical Dictionary for Regulatory Activities; NEC = not elsewhere classified; SMQ = Standardized MedDRA Query' TdP = Torsades de Pointes.

#### **5.13.4. Clinical Laboratory Evaluation**

Laboratory measurements will be analyzed using continuous data (change from baseline) and categorical or ordinal data (proportion of treatment-emergent abnormalities).

If there are multiple records of laboratory measurements at baseline or postbaseline visit, the last record will be used.

Summaries and analyses of continuous data (change from baseline) will be performed using both conventional and International System of Units (SI units).

Change from baseline to each post-baseline visit at which laboratory measurements are taken and change from baseline to the last observation will be summarized and compared between treatment groups using an ANCOVA model. For each lab analyte, the rank-transformation will be applied to the change from baseline for all subjects and all visits prior to analysis. Similarly, an independent rank-transformation will be applied to the baseline values prior to analysis. The model for the fixed effects will include terms for baseline value, treatment and age. This analysis will be done separately for each laboratory analyte.

Treatment differences in the proportion of subjects with treatment-emergent high or treatment-emergent low or treatment-emergent abnormal laboratory values at (1) anytime and (2) each post-baseline visit will be assessed using Fisher's exact test. Treatment-emergent high or low laboratory abnormality will be based on SI unit. For each laboratory analyte, only subjects who were low or normal at baseline and have at least one post-baseline measurement will be included in the denominator when computing the proportion of subject with treatment-emergent high values. Similarly, only subjects who were high or normal at baseline and have at least one post-

baseline measurement will be included in the denominator when computing the proportion of subject with treatment-emergent low values. In addition, treatment differences in the proportion of subjects who were normal at baseline and change to abnormal high or abnormal low values at any post-baseline visit will be summarized.

For urinalysis parameters, baseline to post-baseline shifts will be summarized at each visit. Likelihood ratio chi-square tests will be used to compare increase, no change and decrease shifts in urinalysis parameters between treatment groups at each visit.

For all laboratory analytes, frequencies of subjects with notable changes (that is, increases or decreases of a prespecified amount unique to each analyte) from baseline to each postbaseline visit were also summarized for all subjects and stratified by low, normal, or high at baseline.

The proportion of subjects with treatment-emergent clinically significant changes from a low value or normal value at all baseline at any time in alanine aminotransferase (ALT), alkaline phosphatase (ALP), and total bilirubin will be summarized by treatment group. Abnormal criteria for treatment-emergent clinically significant changes are presented in [Appendix 2](#). Significant changes of interest for hepatic laboratory values are: ALT  $\geq 3$  x upper limit of normal (ULN), total bilirubin  $\geq 2$  x ULN, alkaline phosphatase (ALP)  $> 2$  x ULN, ALT  $\geq 5$  x ULN, ALT  $\geq 10$  x ULN, and total bilirubin  $\geq 2$  x ULN. Additionally, Hy's Law analysis will be conducted by comparing treatment groups with regard to the proportion of patients with (ALT  $\geq 3$  x ULN OR aspartate aminotransferase (AST)  $\geq 3$  x ULN) AND total bilirubin  $\geq 2$  x ULN. Comparisons between treatment groups will be carried out using Fisher's exact test.

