9.4.6. Safety Monitoring

Lilly will periodically review evolving aggregate safety data within the study by appropriate methods. An AC will be designated for at least one interim evaluation of unblinded safety data from Study LLCF (Section 10.3.7).

If a study patient experiences elevated ALT \geq 3X ULN, ALP \geq 2X ULN, or elevated TBL \geq 2X ULN, hepatic laboratory tests (Appendix 4) must be repeated within 3 to 5 days including ALT, AST, ALP, TBL, direct bilirubin, gamma-glutamyl transferase, and creatine kinase to confirm the abnormality and to determine if it is improving or worsening. If the abnormality persists or worsens, clinical and laboratory monitoring must be initiated by the investigator and in consultation with the study medical monitor. Monitoring of ALT, AST, TBL, and ALP must continue until levels normalize or return to approximate baseline levels.

Additional safety data must be collected via the case report form (CRF) if 1 or more of the following conditions occur:

- Elevation of serum ALT to ≥5X ULN on 2 or more consecutive blood tests
- Elevated serum TBL to ≥2X ULN (except for cases of known Gilbert's syndrome)
- Elevation of serum ALP to >2X ULN on 2 or more consecutive blood tests
- Patient discontinued from treatment due to a hepatic event or abnormality of liver tests
- Hepatic event considered to be a SAE

See Appendix 4, for hepatic eCRFs that must be completed for these patients.

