### **5.13.5. Vital Signs and Other Physical Findings**

Vital sign measurements and weight will be analyzed using continuous data (change from baseline) and categorical data (proportion of potentially clinically significant changes).

If there are multiple records of vital sign or weight measurements at baseline or postbaseline visit, the last record will be used. Summary statistics will be presented for observed values at baseline and for change from baseline results at each scheduled postbaseline visit. Systolic and diastolic blood pressure and pulse (collected in sitting position), orthostatic diastolic and orthostatic systolic blood pressures and orthostatic pulse (measurement after 5 minutes in the supine position minus that after 3 minutes in the standing position), temperature, and weight by treatment group for all subjects in the safety population will be summarized.

With the large number of the scheduled vital sign visits, the MMRM model is not suitable for the change from baseline comparison of treatments due to computational challenge. Change from baseline to each post-baseline visit at which vital signs are taken will be assessed using an ANCOVA model with treatment and as independent factors and baseline value and age as covariates in the model. This analysis will be done separately for each vital sign parameter and weight.

The incidence of treatment-emergent abnormal high or low vital signs and weight will be presented by treatment group and visit. Treatment-emergent vital sign evaluations are defined for evaluations collected after the initiation of study medication. Abnormal criteria for

postbaseline vital signs and weight are presented in [Appendix 3](#). Any vital sign or weight meeting the criteria will be considered abnormal. Treatment differences in the proportion of subjects with treatment-emergent abnormal high or low vital signs and weight will be assessed between treatment groups using Fisher's exact test at (1) any time (2) post-baseline visit.

For each vital sign at each post-baseline visit, only subjects who had a baseline result and had a nonmissing result at that post-baseline visit will be included in the denominator when computing the proportion of subjects with treatment-emergent high, low, or abnormal values.

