### **5.13.6. Electrocardiograms**

Electrocardiogram measurements will be analyzed using continuous data (change from baseline) and categorical data (proportion of treatment-emergent abnormalities).

Since ECG is measured in triplicates, the average of triplicates will be used at baseline and each visit. If there are multiple records after averaging ECG triplicates within a visit, the last record of averages will be used.

The analysis will be done for the following ECG measurements: heart rate, PR, QT, QTc, and RR intervals and QRS duration. All analyses of QTc will be carried out using the Fridericia correction (QTcF) method. These summaries will include data from each visit ECG measures are performed. Change from baseline to each post-baseline visit at which ECG measurements are taken and change from baseline to last observation will be assessed using an ANCOVA model. The model for the fixed effects will include terms for the following independent effects: baseline age, baseline ECG score, and treatment. This analysis will be done separately for each ECG parameter.

Incidence of treatment-emergent abnormal ECGs will be assessed by comparisons at (1) anytime and (2) each post-baseline visit between treatment groups with Fisher's exact test. For analyses of treatment-emergent abnormal ECGs, baseline will be considered as all visits before the initiation of drug dose.

Abnormal ECG criteria and criteria for abnormal QTcF prolongation are presented in [Appendix 1](#).

Treatment-emergent high ECG parameters (heart rate, PR interval, QRS duration, QT and QTcF intervals) are the values which are low or normal at all baseline visits and fall into the high

abnormal categories post-baseline. Similarly, treatment-emergent low ECG parameters (Heart Rate, PR interval, QRS duration) are the values which are high or normal at all baseline visits and fall into the low abnormal categories above.

In addition, treatment differences in the proportion of subjects who have normal baselines with a change to abnormal high or abnormal low values at any post-baseline visits will be summarized.

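### The SAP's last-record rule for laboratory data does not exempt the abnormality counts, so a mandated repeat liver test filed under the same visit can displace the value that triggered it

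*SAP*

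**What the plan says.** SAP 5.13.4 opens by announcing two kinds of laboratory analysis: continuous change from baseline, and categorical or ordinal analysis of treatment-emergent abnormalities. The next sentence is the record-selection rule: "If there are multiple records of laboratory measurements at baseline or postbaseline visit, the last record will be used". Later in the section, differences in "treatment-emergent abnormal laboratory values at (1) anytime and (2) each post-baseline visit will be assessed using Fisher's exact test". The hepatic counts follow: ALT ≥3, ≥5 and ≥10×ULN, total bilirubin ≥2×ULN, ALP >2×ULN, and a Hy's Law count of ALT or AST ≥3×ULN together with total bilirubin ≥2×ULN. None of these counts has a record-selection rule of its own.

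Protocol 9.4.6 says that after ALT ≥3×ULN, ALP ≥2×ULN or total bilirubin ≥2×ULN, the hepatic tests "must be repeated within 3 to 5 days including ALT, AST, ALP, TBL", along with other analytes, to confirm the abnormality and its direction.

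SAP 5.13.5 has a parallel rule for vital signs and weight ("If there are multiple records of vital sign or weight measurements at baseline or postbaseline visit, the last record will be used"). SAP 5.13.6 has one for ECGs: after triplicates are averaged, "the last record of averages will be used".

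**The concern.** For a by-visit mean, taking the last record is a harmless convention. For a count of patients who ever crossed a threshold it can cause trouble, because the second record is not random. The protocol creates it because the first value crossed a threshold, and a normal value triggers no repeat. If both records sit under one visit label, the rule keeps the repeat and sets aside the value that prompted it.

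At stake is the completeness of the between-arm liver tables. A transient elevation could be missing from the treatment-emergent and hepatic-threshold counts. A patient meeting both Hy's Law components at the first draw could be missed if either component has fallen by the repeat. Liver disorders are an adverse event group of special interest in SAP Table LLCF.SAP.3, so these tables will be read closely.

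**Working it through.** The plan gives no figure on this point, so there is nothing to reproduce. The check sets the passages side by side and then asks what can be said about size.

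**1. Do the repeat triggers match the counted thresholds?**

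| Test | Repeat trigger (Protocol 9.4.6) | Counted (SAP 5.13.4) |
|---|---|---|
| ALT | ≥3×ULN | ≥3, ≥5, ≥10×ULN |
| ALP | ≥2×ULN | >2×ULN |
| Total bilirubin | ≥2×ULN | ≥2×ULN |
| AST | none on its own | ≥3×ULN, as a Hy's Law component |

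They match almost exactly, apart from AST alone.

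**2. What does the rule do?** Take a patient whose only ALT ≥3×ULN is the first value.

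| Repeat | Filed under the triggering visit | Separate unscheduled visit, included in the any-time count |
|---|---|---|
| <3×ULN | not counted | counted |
| ≥3×ULN | counted | counted |

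Only the top-left cell loses the patient. The same logic applies to a fall from one ALT category to a lower one, and to either Hy's Law component. If the repeat is worse than the first value, the rule keeps the worse value.

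**3. Do the documents say which column applies?** No. The SAP has no rule that maps safety records to visits and none for unscheduled safety records. The Schedule of Activities gives visit tolerances of ±5 days (Week 2), ±7 days (the chemistry visits from Week 4 to Week 36) and ±10 days (Week 52). For tolerance T, the first draw can fall on 2T+1 days and the repeat can come 3, 4 or 5 days later. That gives 3(2T+1) combinations, of which 3+4+5 = 12 put the repeat outside the tolerance:

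- T = 5: (33 − 12)/33 = 21/33 = 64% stay inside
- T = 7: (45 − 12)/45 = 33/45 = 73%
- T = 10: (63 − 12)/63 = 51/63 = 81%

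These shares assume that records are mapped to visits by date and that all day combinations are equally likely. The tolerance is a scheduling rule, so the figures show that same-visit filing is possible. They do not estimate how often it would happen.

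**4. How large could the loss be?** It is the share of first values that fall below threshold on repeat, multiplied by the share of repeats filed under the same visit. The second factor is unknown and can be anything from 0 to 1. For the first, assume log-normal ALT in ULN units with median m, log-SD s, correlation r between draws, and a k-fold rise present at both draws. With z = [ln 3 − ln(k·m)]/s:

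share falling below 3×ULN = 1 − Φ₂(−z, −z; r)/Φ(−z)

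where Φ is the standard normal distribution function and Φ₂ its bivariate form.

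| k | m = 0.5, s = 0.6, r = 0.9 to 0.8 | m = 0.6, s = 0.7, r = 0.9 to 0.8 |
|---|---|---|
| 1 (background variation only) | 55% to 72% | 45% to 62% |

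For k = 6 the share over both settings is about 11% to 20%, and for k = 10 about 5% to 9%. All of m, s, r and k are assumptions. At k = 1 the chance of ALT ≥3×ULN is about 0.14% to 1.1% per draw, or 0.2 to 1.8 patients per 167, the planned size of the larger arms (Protocol 5.1). Random peaks often disappear on repeat, while sustained elevations mostly do not.

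**The case against.** The strongest reply is that the repeat is not a second record at the same visit at all. Protocol Appendix 5 describes hepatic monitoring tests as unscheduled. SAP 5.11.2 treats unscheduled visits as distinct and excludes them only from the efficacy repeated-measures model, and the safety sections contain no such exclusion. On that reading the first value keeps its own visit and the any-time count picks it up. SAP 5.13.5 also says, for vital signs, "Any vital sign or weight meeting the criteria will be considered abnormal", which suggests that any qualifying record was meant to count. Serious cases have other routes as well: the additional hepatic case report pages in Protocol 9.4.6, and the comprehensive hepatic search in SAP Table LLCF.SAP.3.

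Much of this stands. The loss depends on how repeats are stored, and serious liver cases would not go unseen. But none of these passages sets the record rule aside. The any-time wording gives the period, not the record. The vital-sign sentence defines abnormality without selecting among records, and it does not concern laboratory data. For ALT, the additional pages require ≥5×ULN on consecutive tests unless another criterion is met, so an isolated ALT between 3 and 5×ULN could be missed there.

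A reader might also infer that the rule would halve a true liver signal, for example turning 6 v 0 of 167 patients (Fisher p = 0.030) into 3 v 0 (p = 0.25). The documents do not support that. A loss of half is in line with the background-variation model, which has no drug effect. With a sixfold rise present at both draws, at most about 6 × 0.20 = 1.2 of 6 patients would be lost, even if every repeat were filed under the triggering visit. Nor is it shown that the contrast between arms would shrink. An equal proportional loss leaves the risk ratio unchanged, and losing mainly random peaks could raise it.

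**Conclusion.** The point holds as a conditional gap in the SAP. As written, 5.13.4 lets a mandated repeat displace the liver value that triggered it, provided that the repeat is recorded under the same visit and falls below the threshold. If repeats are stored as separate unscheduled visits that the any-time count includes, that count does not change. The documents do not settle which applies, and a hepatic count should not depend on how a database labels a visit.

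No size can be derived from the documents. Under the assumptions shown, the loss is probably small for sustained elevations and larger for isolated peaks. The planned arm sizes serve as illustration only, since SAP section 3 records that the study ended early.

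A reader might infer that vital signs and ECGs are equally exposed because SAP 5.13.5 and 5.13.6 carry the same rule. The documents do not support that: no repeat after an abnormal value is mandated for either, although Protocol 9.4.1 allows unscheduled ECGs at the investigator's discretion. The concern there is weaker and mainly one of consistency.

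**What to change.** In SAP 5.13.4:

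- Limit the last-record rule to by-visit change-from-baseline summaries.
- For treatment-emergent high and low, hepatic-threshold and Hy's Law counts, use the most extreme value among all scheduled, repeat and unscheduled records in the treatment period. For the by-visit abnormality counts, use the most extreme record assigned to that visit.
- State how repeat and unscheduled records are assigned to visits.
- State whether the two Hy's Law components must come from the same draw, since the section is silent and separate extremes give the broader count.

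The same wording can go into 5.13.5 and 5.13.6 for consistency. The SAP already takes the maximum during treatment for skin measures (5.13.8.2) and for visual acuity and intraocular pressure (5.13.8.3), so the approach is not new to the plan.

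The cost is wording and a maximum or minimum derivation on data already collected. The downside is that counts may rise slightly in all arms, because repeats add chances for an extreme value.

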### **5.13.5. Vital Signs and Other Physical Findings**

Vital sign measurements and weight will be analyzed using continuous data (change from baseline) and categorical data (proportion of potentially clinically significant changes).

If there are multiple records of vital sign or weight measurements at baseline or postbaseline visit, the last record will be used. Summary statistics will be presented for observed values at baseline and for change from baseline results at each scheduled postbaseline visit. Systolic and diastolic blood pressure and pulse (collected in sitting position), orthostatic diastolic and orthostatic systolic blood pressures and orthostatic pulse (measurement after 5 minutes in the supine position minus that after 3 minutes in the standing position), temperature, and weight by treatment group for all subjects in the safety population will be summarized.

With the large number of the scheduled vital sign visits, the MMRM model is not suitable for the change from baseline comparison of treatments due to computational challenge. Change from baseline to each post-baseline visit at which vital signs are taken will be assessed using an ANCOVA model with treatment and as independent factors and baseline value and age as covariates in the model. This analysis will be done separately for each vital sign parameter and weight.

The incidence of treatment-emergent abnormal high or low vital signs and weight will be presented by treatment group and visit. Treatment-emergent vital sign evaluations are defined for evaluations collected after the initiation of study medication. Abnormal criteria for

postbaseline vital signs and weight are presented in [Appendix 3](#). Any vital sign or weight meeting the criteria will be considered abnormal. Treatment differences in the proportion of subjects with treatment-emergent abnormal high or low vital signs and weight will be assessed between treatment groups using Fisher's exact test at (1) any time (2) post-baseline visit.

For each vital sign at each post-baseline visit, only subjects who had a baseline result and had a nonmissing result at that post-baseline visit will be included in the denominator when computing the proportion of subjects with treatment-emergent high, low, or abnormal values.

Summary and analyses of change from baseline in weight will be provided. The proportion of subjects with a weight gain or loss of greater than or equal to 7 percent of baseline body weight will be compared between treatment groups using Fisher's exact test at each visit and at any time. For those subjects exhibiting a weight loss of greater than or equal to 7 percent of baseline body weight, body mass index (BMI) will be tabulated by treatment and compared using an ANOVA model with factors for treatment. In addition, categories of BMI (underweight =  $<18.5$ , normal =  $\geq 18.5 - <25$ , overweight =  $\geq 25$  to  $<30$ , obese =  $\geq 30$ ) will be compared across treatment groups using Pearson's chi-square test at each visit and at any time.

A listing of treatment-emergent abnormal vital signs and weight will also be presented by subject and visit.

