### Appendix 3. Criteria of Potential Clinical Significant Vital Signs and Weight

Parameter	Unit	Observed Value	And/Or	Change Relative to Baseline	Change from Supine to Standing
Systolic Blood Pressure (supine or sitting)	mmHg	$\geq 180$	And	Increase of $\geq 20$	-
		$\leq 90$	And	Decrease of $\geq 20$	-
Diastolic Blood Pressure (supine or sitting)	mmHg	$\geq 105$	And	Increase of $\geq 15$	-
		$\leq 50$	And	Decrease of $\geq 15$	-
Systolic Blood Pressure (supine to standing)	mmHg	$\leq 80$	And	-	Decrease of $\geq 20$
Pulse (supine or sitting)	bpm	$\geq 120$	And	Increase of $\geq 15$	-
		$\leq 50$	And	Decrease of $\geq 15$	-
Orthostatic hypotension (Systolic)	Decrease in systolic blood pressure when going from 5 minutes supine to 3 minutes standing of $\geq 20$ mm Hg or the inability to stand quickly for the measurements due to symptoms of orthostasis				
Orthostatic hypotension (Diastolic)	Decrease in diastolic blood pressure when going from 5 minutes supine to 3 minutes standing of $\geq 10$ mm Hg or the inability to stand quickly for the measurements due to symptoms of orthostasis				
Orthostatic pulse (Tachycardia)	Increase in heart rate when going from 5 minutes supine to 3 minutes standing of $\geq 30$ bpm				
Weight		Not Applicable		Increase of $\geq 7\%$ Decrease of $\geq 7\%$	

---

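### The four orthostatic criteria in SAP Appendix 3 carry no baseline condition, so their treatment-emergent table reports post-dose prevalence rather than incidence

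*SAP*

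**What the plan says.** Three rules in SAP 5.13.5 act together.

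- Timing: "Treatment-emergent vital sign evaluations are defined for evaluations collected after the initiation of study medication".
- Criterion: "Any vital sign or weight meeting the criteria will be considered abnormal", with the criteria in Appendix 3.
- Denominator at each visit: "only subjects who had a baseline result and had a nonmissing result at that post-baseline visit will be included in the denominator". The baseline result has to exist; it does not have to be normal.

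In Appendix 3, the resting systolic, diastolic and pulse rows need both a threshold value and a change relative to baseline, and the weight row is itself a change from baseline. The orthostatic rows differ. Systolic orthostatic hypotension is "Decrease in systolic blood pressure when going from 5 minutes supine to 3 minutes standing of" at least 20 mm Hg, and diastolic is "Decrease in diastolic blood pressure when going from 5 minutes supine to 3 minutes standing of" at least 10 mm Hg; either is also met by inability to stand because of symptoms. Orthostatic tachycardia is a rise of at least 30 bpm on standing. The supine-to-standing systolic row needs a value of 80 or below with a fall of at least 20. All four look only at the visit in question.

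Elsewhere the SAP conditions on baseline. For high laboratory values (5.13.4), "only subjects who were low or normal at baseline and have at least one post-baseline measurement will be included in the denominator". High ECG parameters (5.13.6) "are the values which are low or normal at all baseline visits" before becoming abnormal, and baseline there covers all visits before the first dose.

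Proportions are compared by Fisher's exact test, by visit and at any time, at 2-sided 0.05.

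**The concern.** The SAP describes this table as one of incidence. For the four orthostatic rows it would mix new cases with patients who had the same postural change before their first capsule. The population is 55 to 85 years old, and no exclusion criterion names orthostatic hypotension, so some pre-existing cases are to be expected. Vital signs are scheduled at every visit from 4 to 18, so the any-time analysis gives a pre-existing case up to 15 chances to reappear.

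At stake are the meaning of the reported rate and, under some conditions, the sensitivity of the categorical comparison to a postural effect of the drug.

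**Working it through.** **1. The plan's own figures.** The documents give no rate for orthostatic hypotension, so there is none to reproduce. The planned arm sizes (protocol 5.1) are consistent with the total: 167 + 167 + 45 = 379, against about 380; and 380 × 0.85 = 323, against about 320 completers (protocol 5.2).

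**2. Model.** Let b be the share meeting the criterion at baseline, r the share of those who meet it again after dosing, and p the new-onset rate among the rest. The rate under the SAP rule is

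rate = b·r + (1 − b)·p.

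Among baseline-free patients the rate is p, with n(1 − b) patients per arm. If r is the same in both arms, the risk difference under the SAP rule is (1 − b) times the difference in p.

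**3. Inputs.** From the documents: 167 per arm for 12 mg v placebo, Fisher's exact test, 2-sided 0.05. Assumed, because the documents are silent: b = 10%, 20% or 30%; p = 10% on placebo and 20% on 12 mg; r as shown below.

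**4. Equal recurrence in both arms.** At b = 20% and r = 100%, placebo is 0.20 + 0.80 × 0.10 = 28% and 12 mg is 0.20 + 0.80 × 0.20 = 36%. Power is by exact enumeration of the two binomials.

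| b | r | SAP rule, placebo v 12 mg | Power, SAP rule | Baseline-free n per arm | Power, baseline-free |
|---|---|---|---|---|---|
| 10% | 100% | 19% v 28% | 45% | 150 | 63% |
| 20% | 100% | 28% v 36% | 31% | 134 | 58% |
| 20% | 70% | 22% v 30% | 34% | 134 | 58% |
| 30% | 100% | 37% v 44% | 22% | 117 | 50% |

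At b = 20%, the share of placebo cases that are pre-existing is 0.20/0.28 = 71% with full recurrence, and 0.14/0.22 = 64% with 70% recurrence.

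**5. How likely is high recurrence in the any-time analysis?** If a pre-existing case had a 20% chance of meeting the criterion at each of 15 visits, treated as independent, the chance of being counted at least once is 1 − 0.8^15 = 96%. Fewer attended visits would lower this.

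**6. Recurrence raised by the drug.** New onset stays at 10% v 20%.

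| b | r, placebo v 12 mg | SAP rule, placebo v 12 mg | Power, SAP rule | Power, baseline-free |
|---|---|---|---|---|
| 20% | 50% v 70% | 18% v 30% | 69% | 58% |
| 20% | 60% v 80% | 20% v 32% | 67% | 58% |
| 30% | 50% v 70% | 22% v 35% | 71% | 50% |

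The direction of the power difference therefore depends on an unknown.

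**7. Type I error.** With no drug effect, exact Fisher rejects in 3.8% of trials under the SAP rule (22% in both arms, n = 167) and in 3.1% among baseline-free patients (10% in both arms, n = 134). Neither exceeds 5%.

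**The case against.** **The baseline-adjusted analysis already exists.** SAP 5.13.5 lists orthostatic pressures and pulse among its parameters and fits an ANCOVA of change from baseline at each visit, adjusted for the baseline value, using all patients with data. This stands as a real safeguard. It does not correct the categorical table, and a mean change can miss a threshold effect confined to a minority.

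**The adverse-event analysis already has a baseline condition.** A reader might infer that the gap weakens the blood-pressure group among the adverse events of special interest. It does not: that cluster is built from treatment-emergent adverse events, which must have begun or worsened after randomization (SAP 5.13.2 and 5.13.3).

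**The SAP follows the protocol.** Protocol 10.3.4 asks only for a baseline and a post-baseline observation. That is correct, so this is an inconsistency between safety domains within the SAP and not a departure from the protocol.

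**The power loss is conditional.** It rests on assumed prevalence and on equal recurrence across arms, and step 6 shows it can reverse. The absolute figures also use planned numbers, whereas SAP Section 3 says the study ended early and most patients would lack a Week 52 observation. Exclusion criteria 10 (serious or unstable illness) and 25 (clinically important vital-sign abnormality, by investigator judgement) may lower the baseline prevalence. All of this stands; the powers are illustrations only.

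**Excluding baseline-positive patients drops those who may be most susceptible.** This also stands. A listing would not restore them to any comparison, which is why the fix includes a shift table.

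**Conclusion.** The definitional point holds on the text alone and needs no assumption: for four orthostatic rows, an unchanged pre-dose finding is counted as treatment-emergent, so the table gives post-dose prevalence under a label of incidence. The laboratory and ECG rules in the same SAP avoid this.

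Two stronger readings are tempting and are not supported. One is that pre-existing cases are charged to the drug. They are tabulated in every arm, placebo included, without attribution and without type I inflation. The other is that a true effect is necessarily diluted. Dilution follows if recurrence is equal across arms: at 20% prevalence, 31% to 34% power against 58%. If the drug raises recurrence from 50% to 70%, the SAP rule has the higher power, 69% against 58%.

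The case for changing the rule is therefore a correct and interpretable rate, consistent with the other safety domains. A gain in power is possible but not assured.

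**What to change.** In SAP 5.13.5 and Appendix 3, for the four orthostatic rows only:

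- Define treatment-emergent as the criterion met after the first dose in a patient who did not meet it at any pre-dose visit (Visits 1 to 3), with those patients as the denominator. This mirrors the ECG rule.
- Add a table by arm of baseline status against worst post-baseline status, so that baseline-positive patients remain in a between-arm display.
- Leave the ANCOVA of orthostatic change as planned.

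No new data are needed: protocol 9.4.2 requires supine and standing blood pressure and heart rate, and the Schedule of Activities places vital signs at Visits 1, 2 and 3. The cost is a wording change, a smaller denominator for these rows and one more table.
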